#### **2.4.2 Prior, concomitant and post therapies**

Medications will be coded using the World Health Organization (WHO) Drug Dictionary. The WHO Drug Dictionary version used for reporting the study will be indicated in a footnote on relevant outputs.

Medications will be classified as prior or concomitant as follows:

- Prior medications are defined as medications taken and stopped prior to the date of the first dose of ofatumumab for ofatumumab-treated participants, or prior to the date of the Week 0 visit for healthy control participants.
- Concomitant medications are defined as medications that started on or after the date of the first dose and within 30 days (inclusive) following the date of the last dose of ofatumumab for ofatumumab-treated participants, or on or after the date of the Week 0 visit for healthy control participants. Note the 30-day window post last dose of ofatumumab is not applicable to ofatumumab-treated participants who are ongoing in the study at the time of the Month 18 interim analysis.
  - For ofatumumab-treated participants, this includes medications that started prior to the date of the first dose and ended on or after the date of the first dose (and within 30 days [inclusive] following the date of the last dose) or are indicated as ongoing.
  - For healthy control participants, this includes medications that started prior to the date of the Week 0 visit and ended on or after the date of the Week 0 visit or are indicated as ongoing.

Medications will be categorized into the above classes based on recorded or imputed start and end dates (see [Section 5.1.3](#)).

Prior and concomitant medications will be summarized with frequency counts and percentages by Cohort, Anatomical Therapeutic Chemical (ATC) class and PT using the SAF or HCAS, as appropriate. Concomitant medications will be summarized for the open-label treatment phase, open-label extension period and overall. Tables will show the overall number and percentage of participants receiving at least one medication of a particular ATC class and at least one medication of a particular PT.

Non-drug therapies/procedures will be coded using MedDRA terminology. The MedDRA version used for reporting the study will be indicated in a footnote on relevant outputs. Non-drug therapies/procedures will be classified as prior or concomitant based on recorded or imputed start and end dates as outlined above for medications.

Prior and concomitant non-drug therapies/procedures will be summarized by Cohort, primary SOC and PT using the SAF or HCAS, as appropriate. Concomitant non-drug therapies/procedures will be summarized for the open-label treatment phase, open-label extension period and overall. Tables will show the overall number and percentage of participants

with at least one non-drug therapy/procedure of a particular primary SOC and at least one non-drug therapy/procedure of a particular PT.

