Participants who discontinue study treatment or who decide they do not wish to participate in the study further should NOT be considered withdrawn from the study UNLESS they withdraw their consent (see [Section 9.2](#)). Where possible, they should return for the assessments indicated in the visit assessment schedule ([Table 8-1](#)). If they fail to return for these assessments for unknown reasons, every effort (e.g. telephone, e-mail, certified letter) should be made to contact the participant/pre-designated contact as specified in the 'Lost to Follow-up' [Section 9.1.3](#). This contact should preferably be done according to the study visit assessment schedule.

If the participant cannot or is unwilling to attend any visit(s), and has not withdrawn consent to participate, the site staff should maintain regular telephone contact with the participant, or with a person pre-designated by the participant. This telephone contact should preferably be done according to the study assessment schedule.

After discontinuation from study treatment, at a minimum, in abbreviated visits, the following data should be collected at clinic visits or via telephone/email contact:

- New / concomitant treatments
- Adverse Events / Serious Adverse Events

The investigator must also contact the IRT to register the participant's discontinuation from study treatment.

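### SAP 2.4.2 puts the 30-day post-dose limit on the end date of carried-over medications, so some drugs taken throughout ofatumumab exposure are neither prior nor concomitant

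*SAP*

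**What the plan says.** SAP 2.4.2 opens the rule with "Medications will be classified as prior or concomitant as follows", so there are two classes. The section title also names post therapies, and SAP 5.1.3.2 gives date imputation for them, but no post class is defined.

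For the ofatumumab cohort:

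- **Prior:** "Prior medications are defined as medications taken and stopped prior to the date of the first dose of ofatumumab for ofatumumab-treated participants".
- **Concomitant, main rule:** those which "started on or after the date of the first dose and within 30 days (inclusive) following the date of the last dose of ofatumumab". Here the 30 days limit the start date.
- **Concomitant, carried-over drugs:** "this includes medications that started prior to the date of the first dose and ended on or after the date of the first dose", followed in parentheses by "and within 30 days [inclusive] following the date of the last dose) or are indicated as ongoing". Here the 30 days limit the end date.
- **Waiver:** "Note the 30-day window post last dose of ofatumumab is not applicable to ofatumumab-treated participants who are ongoing in the study". The sentence ties this to the Month 18 interim analysis.

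For healthy controls, a drug carried over the Week 0 visit is concomitant if it ended on or after that visit or is ongoing. There is no upper limit on its end date. Non-drug therapies and procedures are classified by the same rules as medications. Protocol 12.3, which plans these summaries, sets no end-date limit either.

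**The concern.** A limit of last dose plus 30 days makes sense for a start date: a drug begun long after exposure has ended is not concomitant with it. On an end date it works backwards. Whether a drug overlapped with ofatumumab does not depend on how long it continued afterwards, so a late stop date should never remove a drug from the concomitant class.

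At stake is the accuracy of the concomitant medication and non-drug-therapy tables. A background treatment really taken alongside ofatumumab would be left out of the count. The two cohorts, summarised by the same tables, would also follow different rules.

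**Working it through.** The plan gives no figure to reproduce, so the check applies the rule exactly as written.

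**Logic.** Take a drug started before the first dose and stopped after last dose + 30 days.

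1. Prior requires a stop before the first dose. It fails.
2. The main concomitant rule requires a start on or after the first dose. It fails.
3. The carried-over rule requires first dose ≤ end ≤ last dose + 30, or ongoing status. It fails.
4. No third class is defined. The drug is unclassified.

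**Numbers.** The first dose is day 1. The last dose is set at day 510, and at day 150 for an early discontinuer; both are assumptions for illustration. The limits are 510 + 30 = 540 and 150 + 30 = 180.

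| Last dose | Drug start | Drug end | Class as written |
|---|---|---|---|
| 510 | −100 | −1 | prior |
| 510 | −100 | 510 | concomitant |
| 510 | −100 | 540 | concomitant |
| 510 | −100 | 541 | neither |
| 510 | −100 | 600 | neither |
| 510 | −100 | ongoing | concomitant |
| 510 | 2 | 600 | concomitant |
| 150 | −100 | 180 | concomitant |
| 150 | −100 | 181 | neither |

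Over a grid of start days −60 to 0 and end days up to 699, with last dose on day 510, the unclassified records were exactly those ending on day 541 or later: 61 start days × 159 end days = 9,699. That count only shows where the boundary lies; it says nothing about frequency in the trial. With the Month 18 waiver applied, the day 541 and day 600 records become concomitant. With the end-date limit removed, no carried-over record in the grid is unclassified.

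**Can such records reach the database?** There are three routes for participants not covered by the waiver.

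- *Treatment stopped, data still collected.* Protocol 9.1.1 keeps treatment discontinuers in the study unless they withdraw consent, and lists "New / concomitant treatments" among the minimum data collected afterwards. SAP Table 2 sets no data cut-off for those who left the study before the Month 18 visit.
- *Completers who do not enter the extension.* Protocol Table 6-4 ends at Month 17, while other protocol text has dosing until Month 18. With Month 18 at day 540 (Table 8-1), a month is 540 / 18 = 30 days and Month 17 is 17 × 30 = day 510. If that is the last dose, the limit is day 540. The Month 18 window of ±3 days runs to day 543, so a stop date on days 541 to 543 falls in the gap. If the last dose is at Month 18, this route closes.
- *Imputed stop dates.* SAP 5.1.3 turns a missing stop month into December and a missing day into the last of the month, with no cap at last contact stated. A drug stopped during treatment with only the year recorded becomes 31 December and can pass the limit.

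**The case against.** The strongest reply is that the reach is small.

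- The waiver protects every ofatumumab participant still in the study at the Month 18 interim analysis, including those who stopped treatment and stayed.
- Those who leave both drug and study have an end-of-study visit within 7 days of discontinuation (Protocol section 3). A drug still in use then would presumably be recorded as ongoing, and so count.
- Data from the 100-day safety follow-up are kept in source documents only (Protocol Table 8-1, footnote 12), so that visit adds no late stop dates.
- Protocol section 3 makes ofatumumab monotherapy a condition of remaining in the trial, which suggests few stay on without the drug.
- The tables count participants with at least one medication per ATC class or preferred term. A lost record changes a count only if the participant has no other qualifying record there.

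All of this stands and limits the size of the point. It does not close the gap, because each of the three routes can still produce an unclassified record.

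A second reply is that the sub-bullet only illustrates the main definition, so a programmer could apply the evident intent. This is weak: no other sentence admits such a drug, and a programmer will code the dates as written.

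Two stronger readings are tempting. A reader might take the planned 15% drop-out, 118 × 0.15 = 17.7, as a bound of about 18 affected participants. The documents do not support that. The figure is a sample-size allowance for drop-out, whereas the gap needs a stop date recorded more than 30 days after the last dose; those are different groups. A reader might also infer that the interpretation of adverse events is compromised. SAP 2.7.1 does not use the prior/concomitant class, and SAP 2.1 lists all data, so the drug and its dates remain visible.

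**Conclusion.** The rule is wrong as written, and the consequence is minor. For ofatumumab participants no longer in the study at the Month 18 interim analysis, a medication or non-drug therapy started before the first dose and stopped more than 30 days after the last dose belongs to no class. Others may be affected at the final analysis, because the waiver is worded for the interim analysis only. The number of participants or records involved cannot be derived from the documents.

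The effect is confined to the descriptive concomitant medication and non-drug-therapy tables. The textual gap rests on no assumption beyond a literal reading of SAP 2.4.2. Its occurrence in practice rests on late stop dates being entered in the database, on a last dose around Month 17 for some completers, or on imputation of partial stop dates.

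**What to change.** In the ofatumumab sub-bullet of SAP 2.4.2, delete the parenthesis that limits the end date. The rule would then cover drugs for which "this includes medications that started prior to the date of the first dose and ended on or after the date of the first dose", or which are ongoing, matching the healthy-control sub-bullet. Keep the 30-day limit in the main definition, where it applies to start dates. Non-drug therapies inherit the correction.

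The cost is one deletion in the SAP and the matching line of table programming. It needs no new data and changes no efficacy or adverse event result.

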## 2.5 Analysis supporting primary objective(s)

The primary objective is to explore the impact of ofatumumab on the ability to achieve NEDA-3 status in treatment-naïve, very early RRMS patients over an 18 month, open-label study period after a re-baseline of MRI at 6 months.

### 2.5.1 Primary endpoint(s)

The primary endpoint is NEDA-3 (relapse-free, 3-month clinical disability progression-free, MRI activity-free) in Months 6 to 18 (yes/no). The 3 components of the primary endpoint are defined as follows:

- Relapse-free is defined as no confirmed relapses. Partial relapse start and end dates will be imputed as outlined in [Section 5.1.3.3](#). Criteria for the linking/combining of individual relapses is outlined in [Section 5.1.3.4](#).
- 3-month clinical disability progression-free is defined as no clinical disability progression as measured by EDSS (global assessment scale), where 3-month confirmed clinical disability progression is defined as an increase from Month 6 in EDSS (global assessment scale) sustained for at least 3 months. That is, after a scheduled or unscheduled visit at which the participant fulfills the clinical disability progression criteria as outlined in [Table 7](#), all EDSS assessments (scheduled or unscheduled) need to also fulfill the clinical disability progression criteria until the progression can be confirmed at the first scheduled visit that occurs in the absence of relapse (confirmed or unconfirmed) 3 months after the onset of the progression, or later. If a participant fulfills the clinical disability progression criteria based on the single EDSS assessment at Month 18, it will be considered a confirmed clinical disability progression (sustainment for at least 3 months will not be required). If a participant dies due to MS (i.e., EDSS = 10 at any time), it will be considered a confirmed clinical disability progression regardless of the Month 6 EDSS or change in EDSS.

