O = Ofatumumab participant

H = Healthy Control

X = assessment to be recorded in the clinical database or received electronically from a vendor

S = assessment to be recorded in the source documentation only

■ [Redacted]

² Relapse assessment will be performed in scheduled, as well as unscheduled visits as deemed necessary by the Investigator or designee. Assessment can be done on site or via remote procedures

³ Urine β-hCG will be conducted monthly, at home, as well as, at defined clinical visits (scheduled and unscheduled)

[Redacted]

⁴ Assessment during an unscheduled visit will be performed as deemed necessary by the investigator, **except** for vital signs and evaluation of AE, which are mandatory at each visit

⁶ Participants are not required to come to the study site. Remote contact with participants, by site staff around the time of at-home, self-administration of ofatumumab should query about any new or worsening symptoms warranting an unscheduled visit, MS relapse, compliance with study treatment [REDACTED], adverse events, and compliance with contraception requirements (when applicable). The method of contact can be via telephone, email, video conference or text message depending on the preference of each participant

⁷ For the first injection, vital signs should be obtained 30-60 minutes before sc injection and again approximately 60 minutes post-injection

⁸ All lab assessments should be taken prior to dosing at the Day 1 visit. For any later biomarker visits, if the visit coincides with the day the monthly injection is scheduled, the subject should not take the injection in the morning before coming to the site so that the biomarker sample can be drawn before the injection

⁹ Labs must be drawn to allow adequate time for results to be obtained before first study drug administration to ensure participant's eligibility

¹⁰ Urine dipstick: If abnormal send full urinalysis to central laboratory

¹² Data for safety follow-up visit will be captured in source documentation only. Safety follow-up participants are not required to come to study site and lab assessments should be done locally

¹³ Only for participants continuing onto the 12-month open-label extension period

¹⁴ Gadolinium will not be given to healthy controls and gadolinium enhanced T1 MRI imaging will not be conducted in healthy controls

¹⁵ The C-SSRS must be administered at either screening or baseline, then at every on-site visit thereafter until End of Study (EOS)

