8.3.1 MS Relapse Assessment

Participants must be instructed to immediately report new neurological symptoms, re-occurring or worsening of previous symptoms to the Investigator. If a participant reports symptoms that may be consistent with a relapse, an unscheduled visit to the Investigator must be scheduled as soon as possible (whenever possible within 7 days of onset of the symptoms).

The assessment, management and reporting of MS relapse is made by the Investigator. Confirmation of MS relapse and severity grading is based on the [REDACTED]

MS relapse definition

[REDACTED]

Appearance of a new neurological abnormality or worsening of previously stable or improving pre-existing neurological abnormality, separated by at least 30 days from onset of a preceding clinical demyelinating event (Polman et al., 2011). The abnormality must have been present for at least 24 hours and occurred in the absence of fever (< 37.5°C) or a known infection.

Diagnosing MS relapses during the study

A participant may report symptoms indicative of a relapse at a planned visit or at any other time. Participants will be instructed to immediately contact the Investigator if he/she develops new, re-occurring or worsening neurological symptoms. During each remote contact performed during the study, the participant will also be asked whether any such symptoms have occurred between scheduled visits. If a participant reports new neurological symptoms or worsening of previous symptoms, an unscheduled visit is to be scheduled as soon as possible, preferably within 7 days. During this visit, the Investigator will first assess whether the new/worsening neurological abnormality is consistent with the definition of MS relapse above. If so, the standard neurological examination (for the EDSS score) will be performed by the EDSS Rater. If there is any doubt in the opinion of the Investigator, the default must always be to refer the case to the EDSS Rater to perform an EDSS rating. The EDSS rater should perform the EDSS rating the same day as the participant's visit to the Investigator whenever possible. Later EDSS assessments can still be utilized for confirmation of MS relapses but should be avoided to reduce the risk of changes in participant status in between the initial assessment by the Investigator and the EDSS rating by the EDSS rater.

Confirmation of MS relapse

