The definition of a confirmed MS relapse is one accompanied by a clinically relevant change in the EDSS performed by the EDSS Rater, i.e. an increase of at least 0.5 points on the EDSS score, or an increase of 1 point on two functional scores (FSs) or 2 points on one FS, excluding changes involving bowel/bladder or cerebral FS compared to the previously available rating (the last EDSS rating that did not occur during a relapse). Confirmation of MS relapse, based on these definitions, will be done using the EDSS score (provided by the EDSS Rater with level B).

All MS relapses, regardless of if they meet definition for confirmation based on EDSS or not, are reported on the appropriate CRF. Severity of MS relapse will be calculated centrally per criteria in Table 8-2 below. MS relapse should not be reported as an AE/SAE unless, in the judgment of the Investigator it is unusually severe or medically unexpected and warrants specific notification as an SAE (as described in Section 10.1.2).

Table 8-2 Severity of MS relapse

Mild Relapse	Moderate Relapse	Severe Relapse
EDSS increase of 0.5 points	EDSS increase of 1 or 2 points	Exceeding Moderate criteria
or	or	or
1 point FS change in one to three systems	2-point FS change in one or two systems	Exceeding Moderate criteria
	or	or

	1 point change in four or more systems	Exceeding Moderate criteria
--	--	-----------------------------

[figure not shown]
[REDACTED]

[REDACTED]

[REDACTED]

[REDACTED]

[REDACTED]

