12.5 Analysis supporting secondary objectives

12.5.1 Efficacy endpoint(s)

For all efficacy analyses, the FAS will be used. The healthy control set will be used if applicable.

Descriptive statistics will be provided for the following variables:

- Number of relapses during the study
- 3-month disability worsening-free (yes/no) during the study
- NEDA clinical in Months 6 to 18 (yes/no)
- NEDA radiological in Months 6 to 18 (yes/no)
- Change from Baseline in conventional MRI metrics (Gd+ lesion number, new Gd+ lesion number, Gd+ lesion volume, T2 lesion number (Baseline), New/enlarging T2 lesion number (post-Baseline), T2 lesion volume, new unenhancing T1 lesion number, T1 unenhancing lesion volume) by visit/time
- Brain volume loss (BVL) assessment (whole brain and regional) (also obtained in HC for normalization purpose) by visit/time

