## 2.2 Analysis sets

The Full Analysis Set (FAS) will include all enrolled participants that received any study drug.

The Safety Analysis Set (SAF) will be the same as the FAS.

The Healthy Control Analysis Set (HCAS) will include all enrolled healthy control participants. This analysis set will be used in the analysis of data collected from healthy control participants.

The modified FAS (mFAS) will include all participants in the FAS except for those who discontinued treatment prematurely prior to Month 18 for reasons other than lack of efficacy or death, or those who completed their Month 18 visit but missed relapse/EDSS/MRI (Gd+ or

new/enlarging T2 lesions) at Month 6, 12 or 18, unless they showed disease activity (i.e., MRI activity after Month 6 through 18 or relapse/3-month clinical disability progression between Months 6 and 18). The mFAS will be used for NEDA-3, NEDA clinical and NEDA radiological efficacy analyses.

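### A reported relapse that never received an EDSS rating is scored relapse-free, so it can count toward NEDA-3 success in the primary analysis

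*SAP*

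**What the plan says.** - **Primary component.** SAP 2.5.1: "Relapse-free is defined as no confirmed relapses".
- **What confirmation needs.** Protocol 8.3.1: "The definition of a confirmed MS relapse is one accompanied by a clinically relevant change in the EDSS performed by the EDSS Rater". The criterion is a sufficient rise in the EDSS or in functional scores over the last rating made outside a relapse.
- **What is recorded.** Protocol 8.3.1: "All MS relapses, regardless of if they meet definition for confirmation based on EDSS or not, are reported on the appropriate CRF".
- **Procedure for a suspected relapse.** Protocol 8.3.1 asks for an unscheduled visit, at which the Investigator judges whether the symptoms fit the relapse definition. "If so, the standard neurological examination (for the EDSS score) will be performed by the EDSS Rater". Doubtful cases also go to the rater, and "Later EDSS assessments can still be utilized for confirmation of MS relapses".
- **Remote option.** Protocol Table 8-1, footnote 2, on relapse assessment: "Assessment can be done on site or via remote procedures".
- **Missing data in the primary analysis.** SAP 2.2 removes from the mFAS "those who completed their Month 18 visit but missed relapse/EDSS/MRI" at Month 6, 12 or 18, unless disease activity was shown. SAP 2.5.3 and 2.5.4 repeat this. In that text disease activity includes relapse, without the word confirmed.
- **NRI.** SAP 5.1.3.3 scores a participant as a failure when the set of valid relapse, EDSS and MRI assessments in Months 6 to 18 is incomplete.
- **Other analyses.** SAP 2.5.5 plans no sensitivity analysis. None of the four supplementary analyses in SAP 2.5.6 counts an unconfirmed relapse as an event.

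**The concern.** An unconfirmed relapse can be one of two things: a relapse that was rated and did not meet the criterion, or a relapse that was never rated. The first is a negative finding. The second is missing information. SAP 2.5.1 gives both the same favourable score.

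The trial is open-label and single-arm, and its result is one proportion with a confidence interval. A rating that a site fails to obtain can only raise that proportion. No comparator offsets the error, and the interval does not allow for it.

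**Working it through.** **Following one case through the rules.** Take a participant who attends Months 6, 12 and 18 with complete EDSS and MRI, shows no MRI activity or progression, and reports a relapse between visits that is never rated.

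1. No rating means no confirmed relapse (Protocol 8.3.1).
2. No confirmed relapse means relapse-free (SAP 2.5.1).
3. Nothing was missed at Month 6, 12 or 18, so the participant stays in the mFAS (SAP 2.2).
4. All three components are clean, so NEDA-3 is achieved.

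If the same participant stops treatment early for a reason other than lack of efficacy or death, SAP 2.2 and 2.5.3 ask whether a relapse occurred in Months 6 to 18. Taken literally, the unrated relapse counts, so the participant is kept and scored as non-response. One event thus gets opposite scores. SAP 2.5.1 specifies both confirmed and unconfirmed relapses in its disability rule, so the unqualified word elsewhere leaves the intent unclear.

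The relapse-combining rule in SAP 5.1.3.4 falls back on an EDSS date from the relapse CRF page. It has no branch for a relapse with no EDSS.

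**Would a scheduled rating fill the gap?** EDSS target days in the window are 180, 360 and 540 (SAP Table 3), so 180 days apart. A relapse lasts at most 90 days (SAP 5.1.3.4). If onsets are spread evenly (assumed), a scheduled rating falls inside the relapse in at most 90/180 = 50% of cases. Months 9 and 15 do not require a site visit.

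**The plan's own figures.**
- Half-width at 80%: 1.96 × √(0.80 × 0.20/100) = 7.84 points.
- Half-width at 85%: 1.96 × √(0.85 × 0.15/100) = 7.00 points.
- Enrolment: 100/0.85 = 117.6, so 118.

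All three reproduce the stated values. Under the planned Clopper-Pearson method, 80/100 gives 70.8% to 87.3% and 85/100 gives 76.5% to 91.4%.

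**How many could be affected.** The confirmed rate is taken as 0.10 to 0.11 per year (Phase 3 figures in Protocol 1.1 and 4.5) over a 12-month window. Let u be the share of reported relapses with no rating. The documents do not give u, so 10%, 20% and 30% are assumed. Unrated relapses per participant = ARR × u/(1 − u). The share with at least one = 1 − exp(−that rate).

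| u | Unrated per 100, ARR 0.10 | ARR 0.11 | Participants per 100 with at least one |
|---|---|---|---|
| 10% | 1.11 | 1.22 | 1.1 to 1.2 |
| 20% | 2.50 | 2.75 | 2.5 to 2.7 |
| 30% | 4.29 | 4.71 | 4.2 to 4.6 |

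The formula treats every rated relapse as confirmed. If only a share c is confirmed, unrated reports number ARR × u/((1 − u)c), which is more. If the same share c of the unrated relapses would have been confirmed, c cancels. The table is then the number that rating would have turned into failures.

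**Effect on NEDA-3.** Let k be the participants per 100 whose only evidence of activity is an unrated relapse. Each k is scored as non-response, with the exact interval, or excluded, giving (80 − k)/(100 − k) or (85 − k)/(100 − k).

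| k | From 80%, non-response | From 80%, excluded | From 85%, non-response | From 85%, excluded |
|---|---|---|---|---|
| 1 | 79% (69.7 to 86.5) | 79.8% | 84% (75.3 to 90.6) | 84.8% |
| 3 | 77% (67.5 to 84.8) | 79.4% | 82% (73.1 to 89.0) | 84.5% |
| 5 | 75% (65.3 to 83.1) | 78.9% | 80% (70.8 to 87.3) | 84.2% |

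Exclusion moves the estimate by about 1 point at most. It also selects on having had a suspected relapse, so it does not bound the bias.

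**The case against.** The strongest reply is that the protocol does not allow an unrated relapse. Section 8.3.1 asks for a visit, has the rater score any event that fits the definition or is in doubt, and accepts later ratings. This stands. A reader might infer from footnote 2 that remote assessment removes the need for a rating. It does not: it allows the relapse assessment to be remote and says nothing to waive the EDSS. An unrated relapse is a departure from procedure, but the SAP still needs a rule for it.

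Redaction is a further limit. Part of the basis for confirmation in Section 8.3.1 and the text between that section and 8.3.6 are blacked out, so a provision for remote EDSS cannot be excluded. It would make unrated relapses rarer. It would not change SAP 2.5.1, whose definition is readable.

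A reader might also infer that the NRI analysis has the same gap. The documents do not settle this. SAP 5.1.3.3 does not limit its complete set to scheduled visits, so a relapse without its rating could already give a failure. The wording is unclear rather than wrong, and NRI is only supplementary.

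Finally, one might object to counting only confirmed relapses, since Protocol 12.5.1 lists "Number of relapses during the study". That reading is not supported as a fault. Confirmation is defined in the protocol, the cited Phase 3 rates are of confirmed relapses, and the SAP document history logs the narrower secondary endpoint. Counting every report would also bring in false positives in an open-label study. It is useful as a bound, not as a replacement.

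**Conclusion.** The concern holds as a gap in the scoring rule. For a Month 18 completer with clean MRI and disability components, a missing relapse rating is scored as NEDA-3 success. It would go too far to say that missing ratings become success in general: relapse is one of three components, and participants who fail on another are unaffected.

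The size is at most about 1 to 5 points per 100 analysed, always favourable, and below the stated half-width. This rests on an assumed 10% to 30% of reported relapses being unrated, on Phase 3 rates carrying over to this earlier population, and on unrated relapses being as likely to meet the criterion as rated ones. The true number of unrated relapses is unknown and could be zero. The inconsistency between SAP 2.5.1 and SAP 2.2 and 2.5.3 stands whatever that number is.

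**What to change.** 1. **SAP 2.2, 2.5.1, 2.5.3 and 2.5.4:** use one term, relapse or confirmed relapse. State that a relapse reported in Months 6 to 18 with no EDSS rating is not scored relapse-free, and how that participant enters the primary numerator and denominator. Excluding these participants is the weaker choice, for the reason shown above.
2. **SAP 5.1.3.3:** state that such a relapse makes the assessment set incomplete, so that NRI gives No.
3. **SAP 2.5.6:** keep the confirmed-relapse definition for rated relapses. Add one supplementary mFAS analysis of NEDA-3 that keeps participants with an unrated relapse and scores them as non-response and, as a bound, does the same for all reported relapses.
4. **Reporting:** tabulate relapses as confirmed, rated but not confirmed, and not rated. Because later ratings are accepted, define which EDSS counts as the rating.
5. **Protocol:** reconcile Table 8-1 footnote 2 with Section 8.3.1.

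The cost is SAP wording, one flag derived from the relapse CRF and EDSS data, one analysis and one table. The reported proportion may be slightly lower.
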